**Table 1: Overview of Trials to be Included in the Population PK Analysis**

Study No.	Study Title & Design	Brief Description of PK Data
67953964MDD2001	
Title: A Phase 2a Randomized, Double-blind, Placebo-Controlled, Parallel-Group, Multi-center Study Investigating the Efficacy, Safety, Tolerability and Pharmacokinetics of JNJ-67953964 in Subjects with Major Depressive Disorder.
 
Design: The treatment phase of the trial will consist of 3 periods. A placebo lead-in period of concealed duration, after which subjects will enter the double-blind treatment period when they will be randomly assigned to 10 mg JNJ-67953964 q.d. or continue placebo in a 1:1 ratio for 6 weeks. Subjects who complete the treatment period, will then enter the withdrawal period and be treated with placebo for the remaining time of the treatment phase of the study.
	
No. of subjects with PK data available/total no. in study: 71/142 (Planned)
 
PK samples are collected for plasma concentrations of JNJ-67953964 before and 2 hours after dosing on Day 22 (Day 1 Treatment Period), 29 (Trt Week 1), 43 (Trt Week 3) and 64 (Trt Week 6).

LAFA	
Single Ascending Dose, Fasted
 
Cohort 1: 4, 25, 60 mg + placebo (15 subjects)
 
Cohort 2: 2 and 10 mg + placebo (9 subjects)
 
Cohort 3: 4, 10, 25, 60 mg + Fentanyl (10 subjects)
	
No. of subjects with PK data available/total : 30/31
 
PK samples are collected at 0, 0.5, 1, 1.5, 2, 3, 4, 6, 8, 12, 24, 48, 72, and 96 h

LAFB	
Multiple Ascending Dose, Fasted
 
Cohort 4: 2 mg q.d. (9 subjects)
 
Cohort 5: 35 mg q.d. (9 subjects)
 
Cohort 6: 10 mg q.d. + ethanol (10 subjects)
	
No. of subjects with PK data available/total : 28/37
 
PK samples are collected at 0, 0.5, 1, 1.5, 2, 3, 4, 6, 8, 12, 24, 48, 72, 96.0, 120, 144, 168, 192, 216, 264 h

LAFC	
Receptor Occupancy (PET)
 
0.5 mg (1), 2 mg (4), 4 mg (2), 10 mg (4), 25 mg (1 subject)
	
No. of subjects with PK data available/total : 12/12
 
PK sample are collected at 0.5, 1.0, 2.5, 4, 6, 8, 12, 22.5 h

**Table 2: Overview of Trials to be Included in the Exposure-Response Analysis**

Study No.	Study Title & Design	Brief Description of Exposure and Response Data
67953964MDD2001	
Title: A Phase 2a Randomized, Double-blind, Placebo-Controlled, Parallel-Group, Multi-center Study Investigating the Efficacy, Safety, Tolerability and Pharmacokinetics of JNJ-67953964 in Subjects with Major Depressive Disorder.
 
Design: The treatment phase of the trial will consist of 3 periods. A placebo lead-in period of concealed duration, after which subjects will enter the double-blind treatment period when they will be randomly assigned to 10 mg JNJ-67953964 q.d. or continue placebo in a 1:1 ratio for 6 weeks. Subjects who complete the treatment period, will then enter the withdrawal period and be treated with placebo for the remaining time of the treatment phase of the study.
	
No. of subjects with Exposure data available/total no. in study : 71/142 (Planned)
 
Exposure metrics derived from popPK on Day 22, 29, 43, 50, 57 (Trt Week 0, 1, 3, 4, 5 and 6) and 78 (EOS).
 
No. of subjects with MADRS and SHAPS data available/total no. in study : 142/142 (Planned)
 
MADRS and SHAPS assessment at Screening (Week -5 to 0) and on Day 1, 8, 15 (Lead-in Week 0, 1, 2), 22, 29, 43, 50, 57 (Trt Week 0, 1, 3, 4, 5 and 6) and Day 78 (EOS).
 
Safety assessments: All AEs and special reporting situations, whether serious or non-serious, will be reported from the time a signed and dated ICF is obtained until completion of the participant's last study-related procedure, which may include contact for follow-up of safety.

## 3.2. Handling Missing Data

### 3.2.1. Missing Concentration Values

Missing plasma concentration values will be treated as missing and will not be replaced with estimated (imputed) values. In the event of duplicate concentrations (samples from the same subject taken at the same time), all duplicated original values will be retained in the dataset but commented out and an additional data record will be included with the median concentration of the excluded duplicated samples.

### 3.2.2. Missing MADRS or SHAPS scores

Missing on-treatment MADRS total or SHAPS scores will be treated as missing and will not be replaced with estimated (imputed) values. If the baseline MADRS or SHAPS is missing in the source data, its value in the analysis dataset will be populated with median of the treatment baseline for the corresponding lead-in response group (placebo-responder or placebo-non-responder).

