#### 3.1. Description of the Available Data

General information about the studies to be included in the Population PK analysis is summarized [Table 1](#), and for Exposure-Response analysis in [Table 2](#). Further studies may be added as appropriate.

All plasma PK samples with available date and time of both blood collection as well as preceding JNJ-67953964 dose administration will be used for the analysis. Subjects who have not received at least 1 dose of study drug (either JNJ-67953964 or placebo) will not be included in the analysis dataset. PK, MADRS and SHAPS data from subjects with missing dosing information and/or with incomplete dosing may only be included up to the time point of first occurrence of the missing dosing information/incomplete dosing. In case of miss-dosing (e.g. subject took one 5-mg capsule instead of two) the records will be handled as such and not be excluded. Any JNJ-67953964 concentrations before the administration of the first dose of JNJ-67953964 will lead to the exclusion of the subject from the analysis (ie, included in the dataset but commented out).

Baseline is defined as the last observation before the first dose administration of the treatment period (i.e. Treatment baseline) for MADRS, SHAPS and safety parameters. Data from screening and the lead-in period will not be included in the analysis. The primary analysis will be performed on data from the treatment period only.

No records will be deleted from the datasets: records that, for any reason, are excluded from the analysis will be commented out (i.e., including the letter “C” at the beginning of each excluded record or using a designated flag column).

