### **3.2.4. Missing Covariate Values**

If only limited covariates from a subject are missing, data can be imputed with one of the following methods:

- For a given covariate, if no more than 10% of all subjects in the analysis population have missing values, then these missing values will be imputed with the median or mean (for continuous covariates) or mode (for categorical covariates) of the non-missing values from appropriate populations (studies), or
- If predictors are correlated, then the missing data will be imputed based on the model that describes the relationship of each predictor to all other predictors.

In cases where the baseline value of a covariate is missing:

- If the covariate value was recorded for the individual at an earlier assessment period, that earlier value will be carried forward.
- If the covariate was not recorded for the individual at an earlier assessment period, but is available from a later assessment, that later value will be carried backward wherever appropriate.

For categorical covariates values which are missing, a special category may also be assigned which indicates that the covariate is unknown. If necessary other methods for missing covariate imputation may be considered. Any additional methods for handling missing covariates will be described in the final report.

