#### 4.6. MADRS and SHAPS PK/PD Modelling

Exploratory plots of individual  $AUC_{0-24h}$  versus MADRS and SHAPS total score, both absolute and change from baseline, stratified by lead-in placebo-response and by visit will be created. The exposure-response analysis will only be performed for the efficacy endpoints if the exploratory analysis shows a relationship in exposure-efficacy.

The MADRS and SHAPS total score data will be modelled using specific parameters for baseline response, placebo effect, and drug effect, according to the following general equation:

$$y_{ij} = (\theta_1 v_1 + \theta_2 v_2 + \theta_3 v_3 + \theta_4 v_4 + \theta_5 v_5 + \alpha_i) + f_i(v_j, C_i) + \varepsilon_{ij}$$

where  $y_{ij}$  represents the change from baseline MADRS or SHAPS total score for the  $i$ -th subject at the  $j$ -th time point ( $j=1..5$  for the 5 post-baseline visits in Week 1, 3, 4, 5 and 6),  $\theta_{1-5}$  represent the fixed effects for the placebo response at the post-baseline visits, i.e.  $j=1..5$  (with  $v_{1-5}$  denoting indicator variables with value 1 when  $j$  is equal to Treatment Week 1, 3, 4, 5 and 6),  $\alpha_i$  represents the random effect parameter for non-drug-related response,  $f_i(v_j, C_i)$  representing the concentration-effect relationship for JNJ-67953964 in the  $i$ -th subject at the post-baseline visits, i.e.  $j=1..5$  as a function of the exposure metric  $C_i$ , and  $\varepsilon_{ij}$  represents the residual variability associated to measurement  $y_{ij}$ . Baseline is defined as treatment baseline, i.e. last observation before the first dose.

The inter-individual variability (IIV) random effect  $\alpha_i$ , and any random effect within  $f_i$  will be assumed to be normally-distributed, zero-mean, uncorrelated random variables. The residual variability random effects  $\varepsilon_{ij}$  will be assumed to be normally-distributed, zero mean, uncorrelated random variables that are also uncorrelated with respect to  $\alpha_i$ , and any random effect within  $f_i$ . Alternative distributions for the IIV and the residual variability random effects may be considered if needed. If warranted by the data, parametric functions of time (e.g. linear, exponential) may be used to describe the placebo effect.

The exposure metrics to be used in the PK/PD model will be  $AUC_{24h}$  (see Section 4.5). Additional exposure metrics may be tested if the  $R^2$  of the correlation between PK parameters is less than 0.8.

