In case of  $C_{0h}$ , observed pre-dose exposure may be used as an alternative to the model-estimated  $C_{0h}$ .

The drug effect sub-model may be parametrized as a linear, or if the exposure range allows,  $E_{max}$ , sigmoid  $E_{max}$ , or exponential function, as determined by model building criteria (Section 4.9). In case a delay in onset of drug effect will be observed during the exploratory analysis, the delay will be fit using an appropriate delay function, such as a sigmoid. Additional functional forms of the drug effect sub-models may be tested. Baseline MADRS or SHAPS will be tested as covariate on both drug-related and drug-non-related response in order to assess the potential influence of higher/lower baseline disease severity on MADRS and SHAPS change. Gender, race, and age at baseline will also be tested. Lead-in placebo response will be tested as covariate on models based on the full dataset for change from baseline MADRS scores. Lead-in placebo response will not be tested as covariate for change from baseline SHAPS models, as no effect was observed on SHAPS during the lead-in period based on blinded data. Additional parameter-covariate relationships may be tested if required.

Primary analysis on MADRS will be performed on the enriched population (lead-in non-responders). In case no effect on MADRS is found, change from baseline SHAPS total scores will be analyzed on the full dataset. If appropriate, the analysis on MADRS may be repeated on the full dataset, where both lead-in placebo response as well as baseline SHAPS total score will be tested as covariate in the model.

Change from baseline MADRS or SHAPS total scores obtained during the withdrawal period (Day 78) may be explored and included in the model as function of exposure if deemed appropriate.

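### The SAP gives conflicting rules for a missing treatment-baseline MADRS or SHAPS score, and the group median adds avoidable noise to all five change scores of each affected subject

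*SAP*

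**What the plan says.** Four parts of the SAP bear on a subject whose Day 22 score is missing.

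- **3.2.2** (missing MADRS or SHAPS): a baseline absent from the source data is "populated with median of the treatment baseline for the corresponding lead-in response group".
- **3.1** (data): "Baseline is defined as the last observation before the first dose administration of the treatment period". Section 4.6 repeats this for the PK/PD model: "Baseline is defined as treatment baseline, i.e. last observation before the first dose".
- **3.2.4** (missing covariates): for a missing baseline covariate, "If the covariate value was recorded for the individual at an earlier assessment period, that earlier value will be carried forward". The score is such a covariate, since 4.6 says "Baseline MADRS or SHAPS will be tested as covariate on both drug-related and drug-non-related response". The general part of 3.2.4 also permits a median or mean when no more than 10% of subjects lack the covariate.
- **3.1** again: "Data from screening and the lead-in period will not be included in the analysis".

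Own earlier scores are scheduled. Table 2 lists "MADRS and SHAPS assessment at Screening (Week -5 to 0) and on Day 1, 8, 15 (Lead-in Week 0, 1, 2" before the treatment visits, and the protocol's Time and Events Schedule agrees. In the 4.6 model the response "represents the change from baseline MADRS or SHAPS total score for the" i-th subject, at five post-baseline visits (Weeks 1, 3, 4, 5 and 6).

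**The concern.** The SAP does not say which rule governs. If Day 22 is missing and Day 15 is present, one programmer could take Day 15 as the baseline under 3.1, and another could insert the group median under 3.2.2. Both could cite the SAP.

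The choice matters for the affected subject because the baseline is subtracted from every on-treatment score and may also enter the model as a covariate. The median ignores where that subject stood a week earlier. The error is the same at all five visits, so the subject-level random effect in 4.6 can absorb it, and residual plots would not readily reveal it.

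**Working it through.** **Plan's own figure.** SAP 3.2.2 contains none. The protocol's sample size (9.1) is used here only to set the scale. Per arm, 2(0.842 + 1.282)² / 0.45² = 44.6, so 45, as stated. Then 45/0.95 = 47.4, so 48 per arm and 96 in total, as stated. The assumed effect is 0.45 × 11 = 4.95 points.

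**Step 1: value given by each rule (Day 22 missing, Day 15 present).**

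| Rule | Baseline used |
|---|---|
| 3.1 and 4.6, definition | own Day 15 score |
| 3.2.4, missing baseline covariate | own Day 15 score |
| 3.2.4, general option | median or mean |
| 3.2.2 | median of lead-in response group |
| 3.1, exclusion of lead-in data | appears to bar Day 15 |

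**Step 2: propagation.** With true baseline b and imputed baseline b + e, the change at visit j becomes y_j − b − e. All five changes shift by −e.

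**Step 3: size of e.** The documents give no baseline SD, no correlation and no missing rate, so these are assumptions. Let SD_b be the within-group baseline SD, ρ the Day 15 to Day 22 correlation, and d the mean drift between those days.

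- Group median: error = SD_b
- Own last score: error = sqrt(2·SD_b²·(1 − ρ) + d²)
- Prediction from own last score: error = SD_b·sqrt(1 − ρ²)

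For SD_b = 6 and d = 0, in points:

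| ρ | Median | Own last score | Prediction |
|---|---|---|---|
| 0.3 | 6.0 | 7.1 | 5.7 |
| 0.5 | 6.0 | 6.0 | 5.2 |
| 0.6 | 6.0 | 5.4 | 4.8 |
| 0.7 | 6.0 | 4.6 | 4.3 |
| 0.8 | 6.0 | 3.8 | 3.6 |
| 0.9 | 6.0 | 2.7 | 2.6 |

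Carry-forward breaks even with the median at ρ = 0.5 + d²/(2·SD_b²). This is 0.50 without drift. With a 2-point drift it is 0.5 + 4/72 = 0.56 at SD_b = 6 and 0.5 + 4/32 = 0.63 at SD_b = 4. Prediction has the smaller error at any non-zero correlation.

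**Step 4: effect on the Week 6 contrast.** Let s be the SD of the Week 6 score and r its correlation with baseline. A change SD of 11 requires s² + SD_b² − 2·r·s·SD_b = 121. With SD_b = 6 and r = 0.4, s = 11.93 and s² = 142.2. For an imputed subject the change variance is:

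- median: s² = 142.2
- own score, ρ = 0.7: 142.2 + 36 − 2 × 11.93 × 6 × 0.4 × 0.7 = 138.2

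With 10% missing, the SE ratio is:

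- median: sqrt((0.9 × 121 + 0.1 × 142.2)/121) = 1.009
- own score: sqrt((0.9 × 121 + 0.1 × 138.2)/121) = 1.007

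With r = 0.6, s = 13.50 and s² = 182.2. The median ratio is then sqrt((108.9 + 18.2)/121) = 1.025. The own-score variance is 182.2 + 36 − 68.0 = 150.2, with ratio 1.012.

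A simulation agrees (48 per arm, effect 4.95, 4,000 runs, SD_b 4 or 6, ρ 0.6 to 0.9, r = 0.4). With 2 to 10% missing, the SE rose by 0.3 to 1.1% with the median and by at most 0.7% with the own score. At SD_b = 6, ρ = 0.7 and 10% missing, the SEs were 2.236 with full data, 2.261 with the median and 2.249 with the own score. The mean difference stayed between −4.92 and −4.97 for every method.

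The ordering at this level is not fixed. Carry-forward gives the smaller SE when ρ exceeds SD_b/(2·s·r), which is 6/(2 × 11.93 × 0.4) = 0.63 at r = 0.4 and 6/(2 × 13.50 × 0.6) = 0.37 at r = 0.6.

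**The case against.** **There may be no conflict.** Read literally, 3.1 makes Day 15 the baseline when Day 22 is missing. Section 3.2.2 would then apply only when no pre-dose score exists, which is where a median is reasonable. This is the best argument on the other side, and it would make the remedy a clarification. It does not remove the need for one. Section 3.2.2 requires the subject's lead-in response group, which presumably rests on lead-in MADRS scores, so for MADRS the rule would almost never operate. The lead-in exclusion in 3.1 also steers an analyst away from Day 15.

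**The specific rule governs, and 3.2.4 allows a median too.** Both are fair, and 3.2.4 alone does not contradict 3.2.2. The tension with the baseline definition in 3.1 and 4.6 remains.

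**The exclusion of lead-in data is a reason for the median.** It is plausible, but the SAP does not apply it absolutely. Lead-in response chooses the median's group in 3.2.2 and is a possible covariate in 4.6.

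**Carry-forward may be worse.** This stands for ρ below about 0.5, or higher with drift. Drift is possible, since protocol 9.1 expects 25% placebo response during the lead-in. A Day 8 score would be older still. This is why a prediction from own scores belongs among the options.

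**A false baseline-change relation.** A reader might infer that moving a subject to the group centre distorts the baseline slope. It does not, because a subject at the centre has little leverage. In a simulation with 72 subjects, SD_b = 6, ρ = 0.6, 10% missing and a true baseline to Week 6 slope of 0.4, the slope of change on baseline was −0.597 with full data, −0.598 with the median and −0.613 with the own score. The median only widened the slope's sampling SD, from 0.182 to 0.192.

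**Conclusion.** The point holds as a minor one. The SAP's rules for a missing treatment baseline need to be reconciled. The median adds noise to the affected subject's change scores, and the subject's own scheduled scores could reduce it if they are sufficiently correlated with Day 22.

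Three stronger conclusions are tempting and are not supported:

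- **Bias in the drug effect.** The baseline visit precedes the first treatment-period dose under concealed assignment, so missingness should not depend on arm, and the simulated difference was unbiased.
- **A threat to the protocol's primary result.** Section 3.2.2 belongs to the exposure-response plan. That model is exploratory and is run only if plots suggest a relationship. The primary MMRM in protocol 9.2.1 is not involved.
- **That every subject has Day 1, 8 and 15 scores.** They are scheduled, with planned numbers only.

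Missing baselines should be rare, because randomisation is stratified by lead-in response and SHAPS (protocol 6.3), which should require scores near that time. At 10% missing, the loss is about 1 to 3% of the standard error, and the difference between imputation methods is smaller. All sizes rest on the assumed SD, correlations, drift and missing rates.

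**What to change.** In SAP 3.2.2, state one order of precedence for a missing treatment-baseline MADRS or SHAPS:

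1. The subject's own last pre-dose score, or a prediction from the subject's own lead-in scores. Choose one in advance. Prediction is safer if the week-to-week correlation may be low or scores drift.
2. The lead-in response group median, only if no own pre-dose score exists.

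Add that the lead-in exclusion in 3.1 does not bar this use, and that 3.2.2 rather than 3.2.4 governs the baseline score when it serves as a covariate. Flag imputed baselines in the dataset, report their number, and repeat the model without those subjects.

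The cost is a short SAP edit, one flag variable and one extra model run. No new data collection is needed, because the lead-in scores are already scheduled.

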### **3.2.3. Missing Date and Time Records**

Concentration records with the following missing information will generally be excluded from the analysis: 1) recorded sampling date and time; 2) dosing information immediately prior to the sample collection time; 3) irresolvable discrepancy between recorded sampling date/time or dosing date/time.

MADRS or SHAPS total score values with the following missing information will generally be excluded from the analysis: 1) recorded assessment date; 2) dosing information on the assessment day; 3) irresolvable discrepancy between recorded MADRS or SHAPS assessment date or dosing date.

### **3.2.4. Missing Covariate Values**

If only limited covariates from a subject are missing, data can be imputed with one of the following methods:

- For a given covariate, if no more than 10% of all subjects in the analysis population have missing values, then these missing values will be imputed with the median or mean (for continuous covariates) or mode (for categorical covariates) of the non-missing values from appropriate populations (studies), or
- If predictors are correlated, then the missing data will be imputed based on the model that describes the relationship of each predictor to all other predictors.

In cases where the baseline value of a covariate is missing:

- If the covariate value was recorded for the individual at an earlier assessment period, that earlier value will be carried forward.
- If the covariate was not recorded for the individual at an earlier assessment period, but is available from a later assessment, that later value will be carried backward wherever appropriate.

For categorical covariates values which are missing, a special category may also be assigned which indicates that the covariate is unknown. If necessary other methods for missing covariate imputation may be considered. Any additional methods for handling missing covariates will be described in the final report.

### **3.2.5. Missing Exposure Variable**

If the individual PK parameters cannot be derived due to a lack of consistent or sufficient data, the typical values of PK parameters, taking the individual demographic values into account, will be used to derive the corresponding exposure metrics. If the number of subjects with missing exposure is relatively high (higher than 10%), a sensitivity analysis will be conducted by excluding the subjects with missing exposure.

### 3.2.6. BQL Data

The BQL data may initially be excluded from the estimation of the parameters (the M1 method) but retained in the NONMEM data set. If the amount of BQL is greater than 10%, the likelihood based (M3) method may be considered to evaluate the impact of BQL data on analysis results.

## 4. DATA ANALYSIS

### 4.1. Preliminary Population PK model

The sparse PK samples collected in Study 67953964MDD2001 will be evaluated with an existing population PK model, developed on a selection of Phase 1 data, in order to derive individual exposure metrics as per analysis objectives.

A population PK model was published as part of the analysis of receptor-occupancy (RO) data obtained in the clinical study LAF-C using positron emission tomography (PET). The PK of JNJ-67953964 in the PET study was described by a two-compartment distribution model with a first order absorption including 9 transit compartments. As the PK data in the PET study was limited to 24 hours, it was clear that the elimination was not captured well with this data. Therefore, this model was then updated with the data of the two phase 1 studies available, LAF-A (single doses of 2 to 60 mg) and LAF-B (daily doses of 2, 10 or 35 mg up to 14 days). The preliminary updated model consisted of 6 transit-absorption compartments and inter-individual variability on relative bioavailability F. Parameter estimates of the preliminary updated population PK model are summarized in [Table 3](#). Due to the limited dataset (n=71 subjects, 56 males and 15 females), no covariate analysis was performed. In case a further updated population PK model becomes available by the time of conducting the analysis, the updated model may be used and the details of the model will be provided in the report.

